### 3 OBJECTIVES AND ENDPOINTS

Objectives	Endpoints
Primary	
• To evaluate the safety of SPR001 in subjects with CAH	

• AEs, SAEs, AEs leading to discontinuation/withdrawal, DLTs, and AESIs

• Physical examination findings

• Vital signs

• Changes in ECG

• Changes in clinical laboratory values

• Changes in the C-SSRS and the HADS

Secondary	
• To evaluate the efficacy of SPR001 in subjects with CAH in terms of changes in hormones	

• Changes in ACTH, 17-OHP, androstenedione, and testosterone

Exploratory	
• To evaluate the effect of SPR001 on QoL, metabolic parameters, exploratory adrenal hormones, and sex-specific outcomes in subjects with CAH	

• Changes in QoL as measured using the SF-36, PGIC, bother score, and CAH signs and symptoms interview

• Changes in fasting glucose, HbA1c, fasting insulin, and lipid profile

• Changes in BW and BMI

• Changes in exploratory adrenal hormones

• Changes in TARTs and on semen analysis in male subjects

• Changes in acne, hirsutism, and menstrual cyclicity in female subjects

## 4 STUDY DESIGN

### 4.1 Overall Design

This is a Phase 2 study of SPR001 for the treatment of classic CAH that will provide 12 weeks of open-label treatment to eligible subjects. To be eligible for this study, an individual must either have completed Study SPR001-201 or meet eligibility criteria for SPR001-naïve subjects (see [Section 5.2](#)). The expected duration of study participation for each subject is up to approximately 7 months. This includes a screening period of 12 weeks, a treatment period of 12 weeks, and a safety follow-up period of 30 days.

Initial subjects who enroll in this study will be treated with SPR001 at 400 mg QD during the treatment period. For subjects who enroll later on in this study, the dose strength may be increased or decreased (by no more than 2-fold) and/or the dose regimen may be adjusted (e.g., to BID dosing, a regimen being tested in Study SPR001-201). In general, subjects are expected to complete the study at the dose strength and on the dose regimen at which they started the study, unless they experience a clinically significant AE that would warrant a dose reduction.

An SRC will review the available safety, PK, and PD data from Study SPR001-201 Cohorts B/C/D and from this study on an ongoing basis and provide recommendations to the Sponsor, who will ultimately decide on any dosing adjustments in this study.

The Schedule of Activities is provided in [Section 1.3](#). Study visits will occur every 2 weeks during the treatment period and should be scheduled for the morning, to accommodate 8am laboratory assessments. Study visits for screening and at Day 1 (baseline), Week 4, Week 8, and Week 12 (end of treatment) will be conducted as outpatient clinic visits. Study visits at Week 2, Week 6, and Week 10 may be conducted as either outpatient clinic visits or in-home visits by qualified study personnel. A final safety follow-up outpatient clinic visit will occur 30 days after the last dose of study drug.

To reduce subject burden, the final safety follow-up visit in Study SPR001-201 for subjects completing that study and rolling over into this study may coincide with the screening visit of this study (with any overlapping assessments conducted only once). Subjects who completed the final follow-up visit in Study SPR001-201 >3 months before screening in this study and subjects naïve to SPR001 must complete anew all specified screening assessments for this study. Subjects will maintain a stable dose and regimen of glucocorticoids throughout this study.

### 4.2 Scientific Rationale for Study Design

In the ongoing Phase 2 Study SPR001-201, subjects with CAH are treated for 2 weeks with any particular dose level of study drug. Given that patients with CAH may require long-term treatment with SPR001 to maintain antagonism of CRF1 receptors in the face of 21-hydroxylase deficiency, a longer-term study of the safety and efficacy of SPR001 is required. This study extends the duration of SPR001 treatment to 12 continuous weeks at a constant dose. The

treatment period of 12 weeks was chosen based on the 3-month duration of the definitive toxicology studies in rats and dogs.

Individuals may qualify for this study as either SPR001-experienced or SPR001-naïve subjects. Individuals who previously received study drug by completing Study SPR001-201 may qualify for this study to receive an extended 12 weeks of study drug. SPR001-naïve individuals may also qualify directly for this study and will provide a bigger sample size for safety data. The Sponsor may decide to restrict later enrollment of SPR001-naïve individuals to those who exhibit certain clinically significant sequelae of hyperandrogenism due to CAH – TARTs in the case of male CAH patients and significant acne, hirsutism, and/or ovulatory dysfunction in the case of female CAH patients. This enriched population may enable better evaluation of exploratory efficacy endpoints to inform future studies of SPR001.

All SPR001-experienced subjects will undergo a washout period before starting study drug in this study. This washout period will include, at a minimum, the 30-day safety follow-up period in Study SPR001-201 and the 12-week screening period in this study. Thus, SPR001-experienced subjects will generally undergo a washout period of at least approximately 4 months between their last dose of study drug in Study SPR001-201 and their first dose of study drug in this study. Furthermore, all subjects coming from Cohort A of Study SPR001-201 will have undergone a washout period of >5 months, given the interval between the completion of Cohort A in early 2018 and the anticipated start date of this study. Based on preliminary population PK analysis of data from Study SPR001-201 Cohort A, a washout period of 32 to 44 days (approximately 5 to 7 times the terminal phase for SPR001) would allow for essentially complete elimination of SPR001.

The schedule of study visits every 2 weeks during the treatment period and the option for some study visits to be in-home visits provides an appropriate balance between closely monitoring subject safety / response to therapy and minimizing subject burden. The 30-day post-treatment washout period in this study allows for adequate safety follow-up and analysis of any HPA axis rebound after the last dose of study drug.

Subjects will take study drug with a meal or after consumption of a standardized snack in order to improve absorption of study drug, since the Phase 1 clinical studies showed minimal study drug absorption when subjects were dosed in a fasted state. Specific dose reduction criteria, strict individual treatment stopping criteria, and appropriate laboratory and medical assessments have been established to ensure subject safety.

### **4.3 Justification for Dose**

Study drug will initially be administered in this study at 400 mg QD. Preliminary clinical data support the safety and potential PD effects of this dose.

A dose of up to 200 mg QD (for 14 days) was clinically assessed in the repeat-dose Phase 1 Study I3C-FW-BLAB in healthy subjects and was well tolerated in that study.

In the ongoing Phase 2 Study SPR001-201 in subjects with CAH, Cohort A has been completed. Dosing for each subject in Cohort A was to start at 200 mg QD (for 14 days) and to escalate to

600 mg QD (for 14 days), then 1000 mg QD (for 14 days). Preliminary data from Cohort A show evidence of CRF1 receptor target engagement (reductions in ACTH) and reductions in key adrenal hormones (17-OHP and androstenedione) at all dose levels tested. Preliminary safety data from Cohort A show SPR001 to be generally well tolerated through 600 mg QD and 4 weeks of dosing, with no SAEs, AEs leading to discontinuation, DLTs, or AESIs and no meaningful changes across clinical laboratory, ECGs, BDI-II and C-SSRS, or physical examination findings. At 1000 mg QD and 6 weeks of dosing, transient elevations in ALT (without any elevations in bilirubin) were observed in 2 subjects (see [Section 2.3.1](#)). Thus, a dose of 400 mg QD is initially planned in this study because this dose lies within the dose range of clinical precedence that has both produced responses in key hormones and been safe and well tolerated.

For subjects who enroll later on in this study, the dose strength may be increased or decreased (by no more than 2-fold) and/or the dose regimen may be adjusted based on ongoing review of the available safety, PK, and PD data from Study SPR001-201 Cohorts B/C/D and from this study by an SRC. For example, the dose regimen may be adjusted to BID dosing, a regimen being tested in Study SPR001-201 that may lower Cmax levels, reduce peak-to-trough fluctuation, and improve diurnal control of elevated hormones in subjects with CAH relative to once-daily dosing.

#### **4.4 End of Study Definition**

A subject is considered to have completed the study if the subject has completed all 12 weeks of treatment. The end of the study is defined as the date of the last follow-up visit of the last subject in the study.

## 5 STUDY POPULATION

This study will enroll up to approximately 24 eligible subjects with classic CAH who either previously completed Study SPR001-201 (see [Section 5.1](#)) or meet eligibility criteria for SPR001-naïve subjects (see [Section 5.2](#)). The study will be conducted at approximately 8 investigative sites in the United States.

All applicable screening evaluations must be completed and reviewed to confirm that potential subjects meet all eligibility criteria. The Investigator will maintain a screening log to record details of all individuals screened and to confirm eligibility or record reasons for screening failure, as applicable.

### 5.1 Eligibility Criteria for Subjects Who Completed Study SPR001-201

#### 5.1.1 Inclusion Criteria for Subjects Who Completed Study SPR001-201

Subjects who completed Study SPR001-201 must meet all of the following criteria to be eligible for this study:

1. Is approved by the Sponsor's Medical Monitor
2. Is on a stable regimen of glucocorticoid replacement for ≥12 weeks before baseline that is expected to remain stable throughout the study
3. If screening for this study occurs >3 months after the subject's final follow-up visit in Study SPR001-201, the subject will have serum 17-OHP measured at screening. On the day of screening, the subject should take any morning glucocorticoid medication after the screening blood draw to allow for an unimpeded assessment of 17-OHP. The subject will be included if screening shows 17-OHP ≥800 ng/dL.
4. Agrees to follow contraception guidelines ([Section 5.3.5](#)). Male subjects must also agree to refrain from donating sperm throughout the treatment period and for 90 days after the last dose of study drug.
5. Is able to understand all study procedures and risks involved and provides written informed consent indicating willingness to comply with all aspects of the protocol

#### 5.1.2 Exclusion Criteria for Subjects Who Completed Study SPR001-201

Subjects who completed Study SPR001-201 will not be eligible for this study if they meet any of the following criteria:

1. Experienced a clinically significant AE (defined in [Section 7.2.7](#)) considered at least possibly related to SPR001 in Study SPR001-201
2. If screening for this study occurs >3 months after the subject's final follow-up visit in Study SPR001-201, the subject will be screened for any clinically significant unstable medical condition, medically significant illness, or chronic disease occurring within 30 days of screening, including but not limited to the following:

- a. A malignancy or <3 years of remission history from any malignancy, other than successfully treated localized skin cancer
- b. Presence of clinically significant renal disease, as evidenced by an eGFR of <60 mL/min/1.73 m^2
- c. Current or chronic history of liver disease, or known hepatic or biliary abnormalities (with the exception of Gilbert's syndrome or asymptomatic gallstones)
- d. Confirmed positive test at screening for active hepatitis B, hepatitis C, or HIV

3. If screening for this study occurs >3 months after the subject's final follow-up visit in Study SPR001-201, the subject will be screened for clinically significant psychiatric disorders by history and from the M.I.N.I. conducted at screening. The subject will be excluded if screening reveals evidence of current major depressive episode, bipolar disorder, schizophrenia, schizoaffective disorder, major depressive disorder with psychotic features, or any other psychotic disorder within the preceding 6 months.

4. Is at increased risk of suicide on the basis of the Investigator's judgment or the results of the C-SSRS conducted at screening and baseline (e.g., C-SSRS Type 3, 4, or 5 ideation during the preceding 6 months or any suicidal behavior within the past 12 months)

5. Has a HADS score >12 for either depression or anxiety at screening or baseline

6. Clinically significant abnormal clinical or laboratory assessments must be discussed with the Medical Monitor to determine eligibility for this study. Abnormal assessments that must be reviewed to determine eligibility include but are not limited to:

- a. Clinically meaningful abnormal ECG results, in the opinion of the Investigator
- b. QTcF >450 msec for male participants or >470 msec for female participants
- c. ALT >2x ULN
- d. Bilirubin >1.5x ULN (isolated bilirubin >1.5x ULN is acceptable if bilirubin is fractionated and direct bilirubin is <35%)

7. Subjects who routinely work overnight shifts require Medical Monitor approval for enrollment

8. Females who are pregnant or lactating

9. Use of any other investigational drug within 30 days or 5 half-lives (whichever is longer) before screening

10. Use of prohibited concomitant medications (see [Section 6.5.2.1](#)), including rosiglitazone, testosterone, and strong inhibitors and/or inducers of CYP3A4 (with the exception of glucocorticoids and birth control), within 30 days or 5 half-lives (whichever is longer) of baseline. Medications metabolized by CYP3A4, 2C8, 2C9, or 2C19, especially those that are sensitive substrates or substrates with narrow therapeutic ranges (see [Section 6.5.2.2](#)), should be discussed on a case-by-case basis with the Medical Monitor to determine whether the medication should be discontinued or may be continued with caution. If

washout is feasible, then the medication should be withdrawn at least 30 days or 5 half-lives (whichever is longer) before baseline.

11. Donation of blood within 60 days before baseline or donation of platelets, white blood cells, or plasma within 15 days before baseline

## 5.2 Eligibility Criteria for SPR001-Naïve Subjects

This study will offer enrollment to SPR001-naïve subjects with eligibility criteria similar to those of Study SPR001-201 but will also seek to include an enriched population of subjects with CAH who exhibit clinically significant sequelae of androgen excess, specifically males 18 to 35 years old with TARTs and adult females with clinically significant acne, hirsutism, and/or ovulatory dysfunction. This study will initially allow enrollment of at least 3 subjects who meet general eligibility criteria for all SPR001-naïve subjects (inclusion criteria in [Section 5.2.1](#) and exclusion criteria in [Section 5.2.3](#)) and who may or may not meet additional inclusion criteria for an enriched population of SPR001-naïve subjects. At any time thereafter, the Sponsor may decide to require all SPR001-naïve subjects who enroll subsequently to satisfy the additional inclusion criteria for an enriched population of SPR001-naïve subjects ([Section 5.2.2](#)). In particular, the study will attempt to enroll an enriched subpopulation of up to approximately 8 male subjects 18 to 35 years old with TARTs, subject to the limitations of enrollment feasibility for this subpopulation and with consideration for the total number of accrued subjects in the study.

### 5.2.1 General Inclusion Criteria for All SPR001-Naïve Subjects

All SPR001-naïve subjects must meet all of the following criteria to be eligible for this study:

1. Male and female subjects  $\geq 18$  years old
2. Has a documented historical diagnosis of classic CAH due to 21-hydroxylase deficiency based on documented genetic mutation or elevated 17-OHP
3. Known or suspected differential diagnosis of any of the other known forms of CAH, including non-classic CAH, requires Medical Monitor approval for enrollment
4. Has serum 17-OHP  $\geq 800$  ng/dL at screening. On the day of screening, the subject should take any morning glucocorticoid medication after the screening blood draw to allow for an unimpeded assessment of 17-OHP.
5. Is on a stable regimen of glucocorticoid replacement for  $\geq 12$  weeks before baseline that is expected to remain stable throughout the study
6. Agrees to follow contraception guidelines ([Section 5.3.5](#)). Male subjects must also agree to refrain from donating sperm throughout the treatment period and for 90 days after the last dose of study drug.
7. Is able to understand all study procedures and risks involved and provides written informed consent indicating willingness to comply with all aspects of the protocol

### **5.2.2 Additional Inclusion Criteria for Enriched Population of SPR001-Naïve Subjects**

After an initial enrollment of at least 3 SPR001-naïve subjects who must fulfill only the inclusion criteria in [Section 5.2.1](#), the Sponsor may decide to require all SPR001-naïve subjects who enroll subsequently to satisfy all of the following additional inclusion criteria for an enriched population of SPR001-naïve subjects:

1. If male, must be 18 to 35 years old, inclusive.
2. If male, must have a diagnosis of TART(s) confirmed via scrotal ultrasound at screening with at least 1 lesion having a diameter  $\geq 4$  mm
3. If female, must have at least one of the following clinically significant sequelae of androgen excess:
  - a. Clinically significant acne defined as an IGA score  $\geq 2$  at screening
  - b. Clinically significant hirsutism defined as an mFG score  $\geq 6$  at screening
  - c. Verifiable history (based on medical records or ability to obtain an accurate history from the individual) of ovulatory dysfunction defined as having at least 1 year of menstrual cycles that last  $\geq 45$  days or having  $\leq 8$  menstrual periods within the past year, if the subject is not on a hormonal contraceptive

### **5.2.3 Exclusion Criteria for All SPR001-Naïve Subjects**

SPR001-naïve subjects will not be eligible for this study if they meet any of the following criteria:

1. Has had a clinically significant unstable medical condition, medically significant illness, or chronic disease within 30 days of screening, including but not limited to:
  - a. A malignancy or  $<3$  years of remission history from any malignancy, other than successfully treated localized skin cancer
  - b. Presence of clinically significant renal disease, as evidenced by an eGFR of  $<60$  mL/min/1.73 m^2
  - c. Current or chronic history of liver disease or known hepatic or biliary abnormalities (with the exception of Gilbert's syndrome or asymptomatic gallstones)
  - d. Confirmed positive test at screening for active hepatitis B, hepatitis C, or HIV
2. Had or has a clinically significant psychiatric disorder either by history or from the M.I.N.I. conducted at screening. The subject will be excluded if screening reveals evidence of current major depressive episode, bipolar disorder, schizophrenia, schizoaffective disorder, major depressive disorder with psychotic features, or any other psychotic disorder within the preceding 6 months.
3. Is at increased risk of suicide on the basis of the Investigator's judgment or the results of the C-SSRS conducted at screening and baseline (e.g., C-SSRS Type 3, 4, or 5 ideation during the preceding 6 months or any suicidal behavior within the past 12 months)
4. Has a HADS score  $>12$  for either depression or anxiety at screening or baseline

5. Clinically significant abnormal clinical or laboratory assessments must be discussed with the Medical Monitor to determine eligibility for this study. Abnormal assessments that must be reviewed to determine eligibility include but are not limited to:
  - a. Clinically meaningful abnormal ECG results, in the opinion of the Investigator
  - b. QTcF >450 msec for male participants or >470 msec for female participants
  - c. ALT >2x ULN
  - d. Bilirubin >1.5x ULN (isolated bilirubin >1.5x ULN is acceptable if bilirubin is fractionated and direct bilirubin is <35%)
6. Has a history that includes bilateral adrenalectomy or hypopituitarism
7. Subjects who routinely work overnight shifts require Medical Monitor approval for enrollment
8. Females who are pregnant or nursing
9. Use of any other investigational drug within 30 days or 5 half-lives (whichever is longer) before screening
10. Use of prohibited concomitant medications (see [Section 6.5.2.1](#)), including rosiglitazone, testosterone, and strong inhibitors and/or inducers of CYP3A4 (with the exception of glucocorticoids and birth control) within 30 days or 5 half-lives (whichever is longer) of baseline. Medications metabolized by CYP3A4, 2C8, 2C9, or 2C19, especially those that are sensitive substrates or substrates with narrow therapeutic ranges (see [Section 6.5.2.2](#)), should be discussed on a case-by-case basis with the Medical Monitor to determine whether the medication should be discontinued or may be continued with caution. If washout is feasible, then the medication should be withdrawn at least 30 days or 5 half-lives (whichever is longer) before baseline.
11. Donation of blood within 60 days before baseline or donation of platelets, white blood cells, or plasma within 15 days before baseline

## 5.3 Lifestyle Considerations

### 5.3.1 Shift Work

Given the daily dosing of SPR001 at 10pm during the treatment period and the blood draws for laboratory assessments at 8am on study visit days, subjects who routinely work overnight shifts require Medical Monitor approval before enrollment.

### 5.3.2 Meals and Dietary Restrictions

Study drug must be consumed with a meal or 5 to 15 minutes after a standardized snack. Standardized snacks will be provided for all dosing days. A list of acceptable alternative food combinations will also be provided.

Subjects will be advised to refrain from consumption of grapefruit or grapefruit juice from 1 day before the first dose of study drug in this study until after the final dose.

### **5.3.3 Caffeine, Alcohol, and Tobacco**

For study visits with 8am blood draws, subjects should abstain from ingesting caffeine- or xanthine-containing products (e.g., coffee, tea, cola drinks, or chocolate) from 5 hours before the blood draw (3am) until after the blood draw. Subjects will abstain from alcohol from 12 hours before the blood draw (8pm) until after the blood draw.

Subjects who use tobacco products should be informed that nicotine-containing products are not permitted while they are at the investigational site.

### **5.3.4 Activity**

Subjects should abstain from strenuous exercise for 8 hours before each study visit.

### **5.3.5 Contraception Guidelines**

#### ***5.3.5.1 Contraception Guidelines for Male Subjects***

A male enrolling in this study who has a female partner of childbearing potential, including those who are breastfeeding, must meet ONE of the following contraceptive criteria:

1. Is sexually abstinent from penile-vaginal intercourse as his usual and preferred lifestyle (abstinent on a long-term and persistent basis) and agrees to remain abstinent throughout the duration of the study
2. Is vasectomized and the absence of sperm has been confirmed
3. Agrees to use a male condom plus partner use of one of the following highly effective contraceptive methods for the duration of the study:
  - a. Combined hormonal contraception (containing estrogen and progestogen): oral, intravaginal, or transdermal
  - b. Progestogen-only hormonal contraception: oral, injectable, or implantable intrauterine device (IUD) or intrauterine system (IUS)
  - c. Bilateral tubal occlusion

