## 1.2 Schema

### 1.3 Schedule of Activities

	Screening Period	Treatment Period								Follow-up/ET
		1  Screening	2 Baseline	3	4	5	6	7	8	
VISIT NUMBER		0	2	4	6	8	10	12	16	
STUDY WEEK										
STUDY DAY 	12 weeks before Day 1	1	15	29	43	57	71	85		Last dose +30 days
Site Visits 	X	X		X		X		X	X	
Home Visits 			X		X		X			
Informed consent	X									
Inclusion/exclusion criteria	X	X								
Demography 	X									
Medical history 	X									
Prior medications 	X									
Concomitant medications 	X	X	X	X	X	X	X	X	X	

 For subjects rolling over from Study SPR001-201, the final safety follow-up visit of Study SPR001-201 may coincide with the screening visit of this study (with any overlapping assessments conducted only once). If a subject completed the final follow-up visit of Study SPR001-201 ≤3 months before the screening period of this study, overlapping assessments conducted at that final follow-up visit need not be repeated at screening for this study. If a subject completed the final follow-up visit of Study SPR001-201 >3 months before the screening period of this study, all screening assessments must be conducted anew, including some additional screening assessments specified for such subjects.

 All visits should be performed on the indicated study days. In cases where this is not possible, the following visit windows apply: ±3 days for Visits 3 to 8 and ±7 days for the safety follow-up visit (Visit 9). All visits, including the early termination visit, should be scheduled for the morning, to accommodate 8am laboratory assessments.

 Study visits for screening; at Weeks 0, 4, 8, and 12; and at final follow-up must be conducted as in-clinic outpatient visits.

 Study visits at Weeks 2, 6, and 10 may be conducted as either in-clinic outpatient visits or in-home visits by qualified study personnel.

 Demographic information needs to be collected only for SPR001-naïve subjects.

 Full medical history and prior medications from the past year will be collected for SPR001-naïve subjects. If a subject completed the final follow-up visit in Study SPR001-201 before the screening period for this study, any significant medical history and medications taken during the intervening period should be captured.

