#### ***5.3.5.2 Contraceptive Guidelines for Female Subjects***

A female enrolling in this study must meet ONE of the following contraceptive criteria:

1. Is postmenopausal  
A postmenopausal state is defined as no menses for at least 1 year without an alternative medical cause. A high FSH level in the postmenopausal range may be used to confirm a postmenopausal state in women not using hormonal contraception or hormonal replacement therapy. However, a single FSH measurement is insufficient to establish a postmenopausal state without at least 1 year of amenorrhea.
2. Is premenopausal but has documentation of one of the following:
  - a. Hysterectomy
  - b. Bilateral salpingectomy
  - c. Bilateral oophorectomy

3. Has only 1 male sexual partner, that partner is vasectomized, and the absence of sperm has been confirmed
4. Is sexually abstinent from penile-vaginal intercourse as her usual and preferred lifestyle (abstinent on a long-term and persistent basis) and agrees to remain abstinent throughout the duration of the study
5. Agrees to use one of the following highly effective contraceptive methods for the duration of the study:
  - a. Combined hormonal contraception (containing estrogen and progestogen): oral, intravaginal, or transdermal
  - b. Progestogen-only hormonal contraception: oral, injectable, or implantable IUD or IUS
  - c. Bilateral tubal occlusion

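### Contraception ends with the 30-day follow-up visit, 2 to 14 days before the protocol's own figure for near-complete drug elimination

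*Protocol*

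**What the plan says.** Protocol Section 5.3.5.1 offers men with a partner of childbearing potential three routes: abstinence, confirmed vasectomy, or this one: "Agrees to use a male condom plus partner use of one of the following highly effective contraceptive methods for the duration of the study". For women, the contraceptive route in Section 5.3.5.2 reads: "Agrees to use one of the following highly effective contraceptive methods for the duration of the study". The abstinence routes for both sexes carry the same limit. No item in 5.3.5 gives a number of days after the last dose.

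The length of a subject's time in the study appears in the synopsis under Study Duration and again in Section 4.1: "This includes a screening period of 12 weeks, a treatment period of 12 weeks, and a safety follow-up period of 30 days". Section 4.1 places the final visit 30 days after the last dose. The Schedule of Activities (1.3) allows 7 days either side and lists a pregnancy test at that visit for women of childbearing potential.

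On elimination, Section 4.2 says that "a washout period of 32 to 44 days (approximately 5 to 7 times the terminal phase for SPR001) would allow for essentially complete elimination". It attributes the figure to a preliminary population PK analysis of Cohort A of Study SPR001-201.

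Section 8.2.7 requires any pregnancy that the site learns of to be reported, with no time limit. The investigator's active collection of information and outcome follow-up cover pregnancies that begin while the subject is participating.

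**The concern.** A limit on conception after an investigational drug normally runs from the last dose and is long enough for the drug to clear. Here it follows the visit schedule instead. The protocol's one elimination figure is longer than the follow-up period, so a woman or a couple can be released while the protocol itself would still expect some drug to be present.

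The safety net thins at the same point. The last scheduled pregnancy test is at the follow-up visit, and active follow-up of a pregnancy stops with participation. A subject who withdraws from the study (Section 7.3) has no stated duty after the last dose.

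The relevant hazard is developmental. Section 2.2.3 reports developmental toxicity in rabbits at 100 and 1000 mg/kg/day.

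The point does not touch postmenopausal or surgically sterile women, women whose only partner is vasectomized, vasectomized men, or men without a partner of childbearing potential.

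**Working it through.** **Inputs.** Scheduled end of participation: last dose + 30 days (4.1). Visit window: ±7 days, so Day +23 to Day +37 (1.3). Elimination time: 32 to 44 days, described as about 5 to 7 times the terminal phase (4.2).

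**Step 1: check the plan's own figures.** 32 / 5 = 6.40 days and 44 / 7 = 6.29 days. Both ends imply nearly the same terminal phase, so the range is self-consistent. Participation is 84 + 84 + 30 = 198 days, about 6.5 months, which agrees with the stated figure of up to about 7 months.

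**Step 2: shortfall.** Shortfall = elimination day − day on which the duty ends, set to zero if negative.

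| Duty ends | Against 32 days | Against 44 days |
|---|---|---|
| Day +23 (earliest visit) | 32 − 23 = 9 | 44 − 23 = 21 |
| Day +30 (scheduled visit) | 32 − 30 = 2 | 44 − 30 = 14 |
| Day +37 (latest visit) | 32 − 37 = −5, so 0 | 44 − 37 = 7 |
| Day +44 (proposed) | 0 | 44 − 44 = 0 |

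No permitted visit day reaches 44.

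**Step 3: residual drug.** Assume that terminal phase means half-life and that decline is first-order. The fraction remaining is 2^(−t/h), with h from 6.29 to 6.40 days.

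| Day after last dose | Fraction remaining |
|---|---|
| +23 | 7.9 to 8.3% |
| +30 | 3.7 to 3.9% |
| +32 | 2.9 to 3.1% |
| +37 | 1.7 to 1.8% |
| +44 | 0.8 to 0.9% |

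Day +30 corresponds to 30 / 6.40 = 4.7 to 30 / 6.29 = 4.8 half-lives.

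**Step 4: compare with the protocol's rule for other drugs.** Sections 5.1.2 and 5.2.3 set washout of prohibited medications at 30 days or 5 half-lives, whichever is longer. Under the Step 3 assumption, 5 half-lives of SPR001 is 32 days at the lower end of the Section 4.2 range. That exceeds 30, so Day +30 narrowly misses this rule as well.

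**Step 5: nonclinical evidence (2.2.3).** The rabbit developmental effects occurred together with maternal toxicity, and the NOAEL was 30 mg/kg/day. In rats, fertility and early embryonic development were unaffected when either sex was treated, up to 1000 mg/kg/day. No exposure margin to the human dose is given, so these doses cannot be turned into a risk at about 4% residual drug.

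**The case against.** The best defence is that the sponsor considered the 30 days. Later in Section 4.2 the protocol calls the 30-day post-treatment period adequate. But it says so for safety follow-up and for studying rebound of the HPA axis, not for conception.

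The benchmark is also borrowed. The 32 to 44 days is approximate and preliminary, and it was written to justify washout between studies. It is not a reproductive-safety threshold. That stands. It is nevertheless the only elimination time in the protocol. Against its lower end the gap is 2 days and less than 1 percentage point of residual drug, so choosing 44 over 32 is a judgement in favour of caution.

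The rat data are reassuring for conception shortly after release. A subject who has withdrawn cannot be monitored. The SAP (4.3) gives a final sample size of 11, so the change may come too late for many of those treated. All three points limit the benefit; none makes the period long enough.

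A reader might infer something stronger: that the duty has no identifiable end, or that it could lapse at the last dose because Section 4.4 states: "A subject is considered to have completed the study if the subject has completed all 12 weeks of treatment". The documents do not support this. That sentence labels completers for disposition. The synopsis and Section 4.1 count follow-up as part of participation, and a pregnancy test is scheduled at the follow-up visit. The other statement in Section 4.4, "The end of the study is defined as the date of the last follow-up visit of the last subject in the study", gives cover at least as long as the subject's own visit.

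A reader might also infer that men need 90 days, because the inclusion criteria require them to "refrain from donating sperm throughout the treatment period and for 90 days after the last dose of study drug". That is an additional duty about donation. No reason is given for its length, it can be met alongside a shorter contraception period, and it does not set a standard for contraception.

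**Conclusion.** The point holds as a minor, cheap safety improvement. Measured against the protocol's own elimination figure, contraception and abstinence end 2 to 14 days early at the scheduled visit, with a range of 0 to 21 days across the permitted window. This rests on reading the limit as each subject's participation through follow-up, which is the natural reading, and on taking the preliminary Section 4.2 range as the benchmark. The residual of about 4% at Day +30 further assumes that terminal phase means half-life.

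The added risk is small, and the documents do not allow it to be quantified. No endpoint, analysis population or test is affected.

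**What to change.** In the abstinence and contraception items of 5.3.5.1 and 5.3.5.2, replace the present limit with: from screening until at least 44 days after the last dose of study drug, including after early discontinuation or withdrawal. If the sponsor prefers a shorter period, 32 days is the minimum consistent with 5 times the terminal phase. Extend the active collection and outcome follow-up in 8.2.7 to pregnancies that begin up to the same date. Check that the consent form, which was not among the documents reviewed, gives that date.

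The cost is protocol and consent wording and about 44 − 30 = 14 more days of contraception than the scheduled visit implies. No visits are added; a phone contact at Day +44 would be optional. Adherence after early withdrawal cannot be monitored, but the subject will have been told the date.
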